## 6.1 Specification of Safety Parameters

### 6.1.1 Unanticipated Problems

The research team has considerable experience in conducting behavioral interventions. A stakeholder advisory board will also provide expertise and guidance to the study team. Problems with meeting recruitment goals will be discussed among study team members, which include personnel from CityLife Neighborhood Clinic, to consider alternative approaches. A minority-owned health communication firm in Philadelphia, MEE Productions, Inc., will also be assisting the study team with recruitment and retention.

### 6.1.2 Adverse Events

We expect very few, if any, adverse events to occur with this protocol. Any psychosocial events that do

---

occur will be reviewed by the PI and addressed immediately. Corrective actions to the protocol, if warranted, will also be undertaken immediately,

## 6.2 Safety Reporting

### 6.2.1 Reporting to IRB

#### 6.2.1.1 *Unanticipated Problems*

All incidents or events that meet criteria for unanticipated problems (UAPs) as defined in Section 6.1.1 Unanticipated Problems require the creation and completion of an unanticipated problem report form (OHR-20).

UAPs that pose risk to participants or others, and that are not AEs, will be submitted to the IRB on an OHR-20 form via the eazUP system within 10 working days of the investigator becoming aware of the event.

UAPs that do not pose risk to participants or others will be submitted to the IRB at the next continuing review.

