#### 6.2.1.2 *Adverse Events*

Grade 1 AEs will be reported to the IRB at continuing review.

Grade 2 AEs will be reported to the IRB at the time of continuing review.

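### A risk-posing unanticipated problem that is also a grade 1-2 adverse event has no expedited IRB deadline, and the section cited as defining such problems gives no criteria

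*Combined protocol and SAP*

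**What the plan says.** Section 6.2.1.1 (Unanticipated Problems) opens with a general duty to fill in a report form, the OHR-20: "All incidents or events that meet criteria for unanticipated problems (UAPs) as defined in Section 6.1.1 Unanticipated Problems require the creation and completion". That sentence sets no submission time. Two timing rules follow:

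- Where there is risk and no AE: "UAPs that pose risk to participants or others, and that are not AEs, will be submitted to the IRB on an OHR-20 form". The clock for this class is "within 10 working days of the investigator becoming aware of the event".
- Where there is no risk, the timing is looser: "UAPs that do not pose risk to participants or others will be submitted to the IRB at the next continuing review".

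Section 6.2.1.2 (Adverse Events) has two sentences. On the lowest grade it says "Grade 1 AEs will be reported to the IRB at continuing review". On the next grade up it says much the same: "Grade 2 AEs will be reported to the IRB at the time of continuing review". Neither makes an exception for an event that is unexpected, related to the study, or also a UAP.

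Section 6.2.1.3 (Serious Adverse Events) sets windows of 2 working days for grade 3-4 events that are unexpected and at least possibly related, 5 working days for unrelated grade 3-4 events, and 1 working day for grade 5.

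Section 6.1.1, to which 6.2.1.1 refers for the definition, covers the team's experience, the advisory board and recruitment. A typical sentence is "Problems with meeting recruitment goals will be discussed among study team members". It gives no criteria for a UAP.

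**The concern.** The two timing rules in 6.2.1.1 leave out a UAP that poses risk and is also an AE. The first rule excludes it because it is an AE, and the second because it poses risk. Only the AE rules remain, and for grades 1 and 2 those lead to continuing review. The order is then reversed within one class of incident: if it poses risk but has produced no AE it is due in 10 working days, whereas if it has produced mild or moderate distress it may wait for continuing review, like a UAP that poses no risk at all.

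This matters somewhat in this trial because section 1.4.1 names anxiety and loss of confidentiality as the risks, and the intervention in section 6 is a group discussion of 6-8 men sharing experiences. If something does go wrong in a session, a low-grade psychosocial event is a plausible result. What is at stake is how soon the IRB learns of it.

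The missing definition is a separate defect. Staff who follow the cross-reference find nothing with which to decide whether an incident is a UAP.

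**Working it through.** There is no sample size or power figure to reproduce. The check maps each type of UAP to its IRB deadline, then does simple arithmetic on the waiting time.

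**Step 1. Deadline by type of event**

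| Event | Governing section | Time to IRB |
|---|---|---|
| (a) UAP, poses risk, not an AE | 6.2.1.1 | 10 working days |
| (b) UAP, poses risk, grade 1-2 AE | none in 6.2.1.1; 6.2.1.2 by default | continuing review |
| (c) UAP, grade 3-4 AE | 6.2.1.3 | 2 working days if unexpected and possibly related; 5 if unrelated |
| (d) UAP, grade 5 AE | 6.2.1.3 | 1 working day |
| (e) UAP, poses no risk | 6.2.1.1 | next continuing review |

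Row (b) has no expedited deadline and shares its timing with row (e). Rows (c) and (d) are faster than row (a). Section 6.2.1.3 lists no window for a grade 3-4 event that is expected and related; such an event would not ordinarily be called unanticipated, so it is left aside here. The gap is row (b) only.

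**Step 2. Length of the wait in row (b)**

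The comparison is row (a): 10 working days is two working weeks, or about 14 calendar days.

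The documents do not give the continuing-review interval. Assume an interval of T days, from 3 to 12 months, with the event date uniform within it. Then the mean wait is T/2, and the share of event dates that wait longer than 14 days is 1 − 14/T.

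- 3 months: T ≈ 91; mean 91/2 ≈ 46 days; share 1 − 14/91 ≈ 85%.
- 6 months: T ≈ 182; mean 182/2 = 91 days; share 1 − 14/182 ≈ 92%.
- 12 months: T = 365; mean 365/2 ≈ 183 days; share 1 − 14/365 ≈ 96%.

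So row (b) is usually, though not always, later than row (a). An event shortly before a scheduled review would reach the IRB within 14 days anyway.

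**Step 3. Sessions that could run in the meantime**

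Section 6 plans 12-15 sessions. The timeline in section 3.4 marks six quarters (1.5 years) for the intervention, and the Study Summary gives 3.5 years of enrollment. Spread evenly:

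- over 1.5 years: 12/1.5 = 8 to 15/1.5 = 10 sessions a year;
- over 3.5 years: 12/3.5 ≈ 3.4 to 15/3.5 ≈ 4.3 sessions a year.

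The mean wait under an assumed annual review is half a year, so about 4-5 sessions on the first schedule and about 2 on the second.

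**Step 4. The definition**

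Section 6.2.1.1 applies to incidents that meet criteria "as defined in Section 6.1.1 Unanticipated Problems". Section 6.1.1 is present and readable, but is on another subject. Section 1.4.1 lists loss of confidentiality as a foreseen risk. Without criteria, the documents cannot settle whether a particular breach is a UAP.

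**The case against.** The best counter-argument is that the incident and the harm are two things. Section 6.2.1.1 speaks of incidents as well as events. A confidentiality breach could be filed as a risk-posing UAP that is not itself an AE, within 10 working days, and the distress it caused could be filed under 6.2.1.2. The exclusion of AEs may have been meant only to route reports between systems, since UAPs go on one form and serious adverse events on another. This reading is available and would close the gap, but the text does not require it, and a reporting rule should not depend on how staff choose to split an incident.

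Other safeguards exist:

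- Section 6.1.2 has the principal investigator review psychosocial events and address them immediately, with any corrective action to the protocol also immediate.
- Section 12.2 requires IRB approval before any amendment is implemented, so a corrective protocol change would reach the IRB.
- Section 13.4 has deviations reported promptly to the IRB, and a breach of the confidentiality duties in 12.5 might qualify.
- Section 6.2.2 sends all AEs to the monitoring committee, and the section on reporting to the funding sponsor sends them to the funder.

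These soften the consequence. None sets an IRB deadline for row (b): the deviation route gives no number of days and needs noncompliance, and the committee's reporting frequency is not in the documents.

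It is also fair to say that anxiety and loss of confidentiality are foreseen, so they are not obviously unanticipated. That stands, and it limits any claim that a typical breach falls in the gap. It also shows why 6.1.1 needs criteria.

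**Conclusion.** The gap is real but narrow. A UAP that poses risk and is also a grade 1-2 AE has no expedited IRB deadline, and the definition on which the rule relies is absent. On an assumed review interval of 3 to 12 months with uniform event dates, the mean wait is about 46 to 183 days against a limit of about 14. The ordering problem does not depend on those figures, except that a review falling due within the 10 working days would remove it for that event.

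Three stronger conclusions might be inferred, and the documents do not support them:

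- That every UAP causing an AE is reported late. Grade 3-5 events have the windows in 6.2.1.3.
- That any harmless incident is reported sooner than a harmful one. A UAP that poses no risk also waits for continuing review, so the comparison holds only for incidents that pose risk.
- That nearly all planned sessions would run before the IRB hears. This needs an annual review, an event just after a review and at the start of the programme, and sessions concentrated in that year at the stated 1-2 per month. Spread over the planned six quarters, 8-10 sessions fall in a year.

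The matter is one of IRB notification in a study that expects few AEs, and has no bearing on power or the primary analysis. Severity is minor.

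**What to change.** In section 6.2.1.1, delete the words that exclude AEs from the 10-working-day rule. Alternatively, keep them and add a sentence that a risk-posing UAP that is also a grade 1-2 AE goes to the IRB within the same 10 working days. State in either case that the shorter windows in 6.2.1.3 still govern grades 3-5, and add a cross-reference in 6.2.1.2.

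In section 6.1.1, replace the recruitment text with the institution's definition of an unanticipated problem, and say how a foreseen risk such as loss of confidentiality is to be classified. The recruitment text can move to section 4.3.

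The cost is a protocol amendment of a few lines. The downside is possibly a few more expedited reports and some overlap, since one grade 1-2 event could then be reportable both as a UAP and as an AE. A sentence saying which report takes precedence would deal with the overlap. The wording should be checked against the institution's reporting policy and its monitoring plan, neither of which is in the documents.

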#### 6.2.1.2 *Adverse Events*

Grade 1 AEs will be reported to the IRB at continuing review.

Grade 2 AEs will be reported to the IRB at the time of continuing review.

#### 6.2.1.3. *Serious Adverse Events*

SAEs will be reported to the IRB on OHR-10 forms via the electronic reporting system (eSAEY) according to the required time frames described below.

Grade 3-4 AEs that are unexpected and deemed to be at least possibly related to the study will be reported to the IRB within 2 working days of knowledge of the event.

Grade 3-4 AEs that are deemed unrelated to the study will be reported to the IRB within 5 working days.

Grade 5 AEs will be reported to the IRB within one working day of knowledge of the event.

All SAEs will be submitted to the IRB at continuing review, including those that were reported previously.

### **6.2.2 Reporting to SKCC DSMC**

All AEs and SAEs, safety and toxicity data, and any corrective actions will be submitted to the DSMC per the frequency described in the SKCC DSMP. The report to the SKCC DSMC will also include any unanticipated problems that in the opinion of the PI should be reported to the DSMC.

### **Reporting to Funding Sponsor**

Any adverse events will be reported to the sponsor of the study, the Department of Defense.

## **7 Study Oversight**

In addition to the PI's responsibility for oversight, study oversight will be under the direction of the SKCC's Data and Safety Monitoring Committee (DSMC). The SKCC DSMC operates in compliance with a Data and Safety Monitoring Plan (DSMP) that is approved by the NCI.

## **8 Clinical Site Monitoring and Auditing**

Clinical site monitoring and auditing is conducted to ensure that the rights of human participants are protected, that the study is implemented in accordance with the protocol and/or other operating procedures, and that the quality and integrity of study data and data collection methods are maintained. Monitoring and auditing for this study will be performed in accordance with the SKCC's Data and Safety Monitoring Plan (DSMP) developed by the SKCC Data and Safety Monitoring Committee (DSMC). The DSMP specifies the frequency of monitoring, monitoring procedures, the level of clinical site monitoring activities (e.g., the percentage of participant data to be reviewed), and the distribution of monitoring reports. Some monitoring activities may be performed remotely, while others will take place at the study site(s). Appropriate staff will conduct monitoring activities and provide reports of the findings and associated action items in accordance with the details described in the SKCC DSMP.

## **9 Statistical Considerations**

### **9.1 Study Hypotheses**

Men who are educated about PCA genetic testing by peer health educators will be less conflicted about their decision to seek genetic testing than men who receive traditional information by mail.

## 9.2 Analysis Plans

**Decisional Conflict to Consider Genetic Testing.** All study variables, such as demographics, PCA knowledge, and outcome responses, will be summarized in tables with descriptive statistics or graphically in data plots at each time they are assessed along with changes in responses over time. We will investigate imbalances in these data for potential confounding of primary and exploratory endpoint analyses and investigate disparities and intervention effect modification in various subgroups of subjects. The primary outcome is decisional conflict regarding genetic testing assessed by the 4-item SURE scale. To compute a summary decisional conflict score, the Likert-scaled responses will be averaged across the SURE item responses provided by a subject completing at least 2 of the 4 questions. The change in decisional conflict scores between baseline and endpoint at 2-months will be calculated and group means for these changes compared between subjects randomized to receive control materials vs. those randomized to receive the peer health education intervention (i.e., by intention to treat). The significance of the difference will be evaluated at the 0.05 level using a two-sided Student's t-test. The assumptions for this test will be carefully evaluated. If the changes are substantially skewed, they will be summarized with group medians and evaluated for significant differences by the nonparametric Wilcoxon's rank sum test. If concerns arise over potential confounding from imbalances in baseline covariates, we will conduct a sensitivity analysis by applying analysis of covariance (ANCOVA) to adjust the comparison for baseline imbalances, including baseline decisional conflict scores.

**Descriptive and Exploratory Analyses.** Exploratory analyses will include estimating the proportion of AA men meeting the NCCN guidelines for genetic testing and computing a 95% confidence interval using the Clopper-Pearson exact method. Summary statistics and qualitative analyses will be used to assess the genetic counseling experience of those subjects accepting the offer for genetic counseling. Additional analyses will include estimating the intervention effect on genetic testing/counseling intentions and uptake, respectively, changes in attitudes toward genetic testing, and understanding of personal genetic test results using discrete variable tests, such as McNemar's test.

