**Study Randomization and Informed Consent.** Those who are eligible to participate will be randomized to either the intervention or the control arm. Men randomized to the intervention arm will be scheduled to attend a health education session hosted at CityLife Clinic or virtually, while men who are randomized to the control arm will receive educational materials about PCA genetic testing in the mail or in person. All men who agree to participate will be read a consent statement over the phone or in person and will verbally agree to consent to participate. A copy of the consent statement will be provided to them for their records.

**Baseline Survey.** All participants will complete a brief baseline questionnaire over the telephone or in person with the study manager. Items to be assessed at baseline include knowledge about prostate cancer, their personal family cancer history, knowledge of genetic testing and screening, attitudes towards genetic testing, subjective norms about genetic testing, decisional conflict about genetic testing, and intentions to seek genetic counseling. Knowledge about PCA genetics and genetic testing will be measured using a 14-item scale, recently published by the study team in a population of men undergoing genetic testing. The measure for decisional conflict will be the SURE Decisional Conflict Scale, a low-literacy validated measure to screen for decisional conflict. The four questions encompass the following with Yes/No responses: (1) Do you feel sure about the best choice for you? (2) Do you know the benefits and risks of your options? (3) Are you clear about which benefits and risks matter most to you? (4) Do you have enough support and advice to make a choice? Demographic data related to age, race/ethnicity, family history of prostate or other cancer, and other pertinent health information will be collected.

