### **Study Intervention.**

*Intervention Arm:* Men who are randomized to the intervention arm will be invited to a peer health education session, either in-person or virtually. Eighty-eight of the 176 men will be randomized to this group, and we will host sessions that attract roughly 6-8 men at a session. Our previous experience conducting peer health education sessions found that 6-8 men was an ideal attendance level, as it allowed for interaction and discussion but did not feel overwhelming. Each session will be facilitated by two peer educators, who can share responsibilities and interact with each other. We expect to offer 12-15 sessions, or roughly 1-2 sessions per month. Sessions will be scheduled at various times of the day and days of the week, to accommodate men with varying schedules and commitments. Each peer educator will be compensated for 2 hours of time to run a session from start to finish, being compensated at \$20/hour.

First, the peer educator will introduce the topic of PCA, so that men understand the disease and how it relates to their health. The educator will lead a discussion regarding PCA risk, family history, PCA genetics, considerations of genetic testing, implications of genetic testing on family and self, and financial and ethical considerations. The discussion is meant to be interactive, with men sharing stories and experiences and peer educators answering questions and clarifying facts. All information will be delivered in a culturally appropriate manner by peer educators who are from the community they are serving. Immediately following the discussion, men will complete a post-survey to measure short-term changes knowledge about prostate cancer and genetic testing, thoughts about cancer, in decisional conflict about genetic testing, attitudes toward genetic testing, subjective norms about testing, and intentions to seek genetic testing. We will also get feedback on the peer-led session.

*Control Arm:* After providing informed consent and completing the baseline survey over the telephone or in-person, eighty-eight men will be randomized to this arm and each man will receive an educational booklet. It is expected that materials will be mailed within 24 hours of the

---

telephone call or provided to the participant in person. The information will cover PCA risk, family history, PCA genetics, considerations of genetic testing, implications of genetic testing on family, and financial and insurance considerations.

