**Endpoint Survey.** All men, regardless of study arm, will complete an endpoint survey. A member of the study team will call each participant two months after either attending a peer education session (intervention arm) or being mailed the educational print materials (control arm). Previous research shows that two months is an adequate amount of time to digest the material and act upon it, if desired. The majority of items on the baseline survey, except for the demographic information, will be repeated on the endpoint survey. Participants who are not reached by telephone will be contacted by mail and by email to attempt to retain the maximum number of participants over time.

**Participant Compensation.** Each man who participates in all study-related activities will receive \$50 over the course of the study. Men in the intervention group will receive \$25 for completing the baseline survey via the mail and \$25 for completing the endpoint survey over the telephone at two-months post-intervention. Men in the control group will receive \$25 in their mailed packet of materials after completion the baseline survey and an additional \$25 for completing the endpoint survey over the telephone at two-months post-intervention.

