## 9.3 Sample Size Considerations

**Sample Size Considerations and Missing Data Analysis.** In a study conducted at Jefferson of 273 older AA subjects at risk of PCA, the SURE decisional conflict instrument showed good reliability (Cronbach's  $\alpha = 0.76$ ) and the summary scores were  $3.77 \pm 0.76$ , on average. A sample size of  $n=75$  per group ( $N=150$  total) is necessary in order to have at least 90% power to detect a difference of at least 0.40 Likert scale units (a moderate, but clinically important, relative effect size of about  $\frac{1}{2}$  standard deviation) in mean decision conflict between control and intervention by

a two-sided t-test with a 5% type I error rate. We plan to over-recruit to 176 men (88 men per arm) to account for ~15% expected attrition. Missing data patterns across all efficacy outcome variables over time will be evaluated and multiple imputation will be considered if the data appear likely to be missing at random. Sensitivity to missing data mechanism assumptions will be evaluated, with methods such as pattern mixture modeling, if more than 10% of data are missing for any outcome variable.

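### The sample size uses the SD of a single summary score, but the primary test is on unadjusted change with no SD of change or correlation stated; baseline-adjusted ANCOVA should be the primary analysis

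*Combined protocol and SAP*

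**What the plan says.** **Primary analysis (9.2).** "The change in decisional conflict scores between baseline and endpoint at 2-months will be calculated and group means for these changes compared" between the randomized arms, by a two-sided Student's t-test at 0.05. Two conditional steps follow. On distribution: "If the changes are substantially skewed, they will be summarized with group medians and evaluated for significant differences by the nonparametric" Wilcoxon rank sum test. On adjustment: "If concerns arise over potential confounding from imbalances in baseline covariates, we will conduct a sensitivity analysis by applying analysis of covariance (ANCOVA", with the baseline decisional conflict score among the covariates. Neither condition has a stated criterion.

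**Sample size (9.3).** In an earlier study of 273 men the summary scores were 3.77 ± 0.76. The section asks for 75 per group to give at least 90% power for a difference of 0.40 units "in mean decision conflict between control and intervention" by a two-sided 5% t-test, and recruits 88 per arm to allow for about 15% attrition. Change is not mentioned. The same section plans to examine missing-data patterns, to consider multiple imputation, and to run sensitivity analyses if more than 10% of an outcome is missing.

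**The baseline score (section 6 and 14.3).** Under Baseline Survey, "All participants will complete a brief baseline questionnaire over the telephone or in person". Under Control Arm, "After providing informed consent and completing the baseline survey over the telephone or in-person, eighty-eight men will be randomized to this arm". Two payment paragraphs read differently for intervention men: Participant Compensation in section 6 pays them "for completing the baseline survey via the mail", while 14.3 ties the same payment to a baseline survey done when the education session takes place.

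**Scoring.** The Baseline Survey text says of SURE: "The four questions encompass the following with Yes/No responses". Sections 9.2 and 9.3 treat the items as Likert-scaled.

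**The concern.** The variance that governs the primary test is the variance of change, which depends on rho. Section 9.3 supplies the SD of a score at one time. The two coincide only at one value of rho (0.5 when the SDs are equal), and the plan neither states nor sources that value. If rho were lower, the planned test would have less than the stated power; if higher, more. Meanwhile the analysis that uses the baseline score most efficiently is held back as a sensitivity analysis, to be run only if somebody becomes concerned about imbalance.

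**Working it through.** **Inputs from the documents:** difference 0.40; SD 0.76 (the ± figure, read as an SD); two-sided 0.05; 75 per arm analysed, 88 per arm randomized (88 × 0.85 = 74.8).

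**Assumptions of this check:** rho from 0 to 0.7; SD 0.76 at baseline and at 2 months; independent men.

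**1. Reproduce the plan's figure.** The normal approximation gives n = 2 × (1.960 + 1.282)² × (0.76/0.40)² = 75.9 per arm; the exact t needs 77. At 75 per arm the noncentrality is 0.40 / (0.76 × √(2/75)) = 3.22 and power is 89.3%. That matches the stated design closely enough to conclude that 0.76 is the SD used.

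**2. Formulas.** With equal SDs:
- SD of change = 0.76 × √(2(1 − rho)), with 2n − 2 degrees of freedom.
- ANCOVA residual SD = 0.76 × √(1 − rho²), with 2n − 3 degrees of freedom.

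The SD of change equals 0.76 when 2(1 − rho) = 1, that is, at rho = 0.5.

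**3. Power (noncentral t).**

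| rho | SD of change | Change, 75/arm | Change, 88/arm | ANCOVA SD | ANCOVA, 75/arm | ANCOVA, 88/arm |
|---|---|---|---|---|---|---|
| 0 | 1.075 | 62.0% | 69.0% | 0.760 | 89.3% | 93.5% |
| 0.3 | 0.899 | 77.2% | 83.5% | 0.725 | 91.9% | 95.4% |
| 0.5 | 0.760 | 89.3% | 93.5% | 0.658 | 95.9% | 98.0% |
| 0.7 | 0.589 | 98.5% | 99.4% | 0.543 | 99.4% | 99.8% |

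The change-score test reaches 90% at rho 0.51 with 75 per arm and at rho 0.43 with 88. Men per arm needed for 90% at rho 0.3, 0.5 and 0.7 are 108, 77 and 47 for change, and 71, 58 and 40 for ANCOVA.

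**4. Does the ordering depend on equal SDs?** No. With baseline SD s0 and endpoint SD s1:
- Var(change) = s0² + s1² − 2·rho·s0·s1
- Var(ANCOVA residual) = s1²(1 − rho²)
- The difference is s0² − 2·rho·s0·s1 + rho²·s1² = (s0 − rho·s1)², which is never negative.

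**5. Does the 89% floor depend on the assumptions?** Yes.
- *Endpoint SD.* With endpoint SD 0.90 (an assumption) and baseline SD 0.76, ANCOVA at 75 per arm gives 77% at rho 0, 81% at rho 0.3 and 88% at rho 0.5. Change at rho 0.5 gives 83%.
- *Independence.* The intervention is delivered in sessions of 6-8 men. Taking 7 per session, clustering in the intervention arm only, and intraclass correlations of 0.05 and 0.10 (both assumed), the design effects are 1 + 6 × 0.05 = 1.3 and 1 + 6 × 0.10 = 1.6. ANCOVA power at rho 0 and 75 per arm then falls to about 85% and 80%.

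**6. Skewed scores.** In simulations with absolute skewness 1 and 2, SD 0.76 and 75 per arm (20,000 trials each), ANCOVA type I error was 0.049 to 0.053, and its power exceeded that of the change score at every rho tried. These runs did not include the Wilcoxon test or the skewness-triggered switch.

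**The case against.** The strongest reply is that nothing is wrong with the planned test. Randomization makes the comparison of changes valid. At rho 0.5 sections 9.2 and 9.3 agree exactly, and if attrition is lighter than planned a rho of 0.43 can be enough. Section 9.2 also names ANCOVA with the baseline score already. All of this stands. A reader might infer that the trial is underpowered; the documents give no rho, so they do not support that. What survives is an unstated assumption, and an available analysis that depends on it much less.

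A second reply is that ANCOVA does not guarantee 89% either. That is right: step 5 shows that the floor needs an endpoint SD of 0.76 and independent men. Only the precision ordering against change is general.

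Third, a reader might infer that the skewness-triggered move to Wilcoxon distorts the type I error. Nothing here quantifies any such harm; the simulations show only that ANCOVA tolerates the skewness tried. The case for fixing the test in advance is one of principle.

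Fourth, a reader might infer that intervention men who never attend will lack a baseline score. The literal wording of 14.3 allows that, but it and Participant Compensation are payment text and may describe how or when the money is handed over. The procedural text under Baseline Survey covers every participant. Any baseline scores that were missing would also fall under the missing-data plan in 9.3. The wording is ambiguous and worth reconciling; a loss of data is not shown.

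**Conclusion.** The point holds as a mismatch between sizing and analysis and as avoidable loss of precision, not as a demonstrated shortfall or an invalid test. With SD 0.76 at both times and independent men, the stated 90% is met by the change score only if rho is about 0.5 or more; at rho 0.3 power is 77% with 75 per arm. ANCOVA stays within 0.7 points of 90% at any rho from 0 up under those assumptions, and at rho 0.5 it reduces the men needed per arm from 77 to 58. Its advantage over change does not depend on the SDs; its absolute power does.

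Every power figure also presumes that 0.76 and 0.40 apply to the score that will be analysed. If Yes/No items are scored 0/1 and averaged, a mean of 3.77 cannot occur and the figures must be redone. The change should be made; the confidence is high on the mismatch and on the ordering of the two analyses.

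**What to change.** **Section 9.2.** Make the primary analysis an ANCOVA of the 2-month SURE score on arm and baseline SURE score, regardless of observed imbalance. Keep the unadjusted change-score t-test as a sensitivity analysis.

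**Section 9.3.** Restate power for that analysis with the assumed endpoint SD, rho and independence written out (about 89% at rho 0, SD 0.76 and 75 per arm), noting that group sessions make independence an assumption. If change stays primary, state and source its SD instead. Recompute once Yes/No versus Likert scoring is reconciled.

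**Secondary.**
- Prespecify the Wilcoxon comparison of changes as a sensitivity analysis rather than a switch triggered by the data.
- Reconcile Baseline Survey, Control Arm, Participant Compensation and 14.3, so that a baseline score obtained before the intervention clearly exists for all randomized men.

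**Cost.** Wording in 9.2 and 9.3, one recalculated power statement and reconciled baseline text. The analysis spends one degree of freedom. No extra men and no new data items are needed, since the baseline decisional conflict score is already planned for all participants, subject to that reconciliation.
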